Kisspeptin Physiology in Patients with Hyperprolactinemia

NCT02956447

Study Protocol and Statistical Analysis Plan

6/14/23

Kisspeptin Physiology in Patients with Hyperprolactinemia

BROAD GOALS

The overall goals of this protocol are to stimulate gonadotropin secretion and folliculogenesis using exogenous kisspeptin administration.

SPECIFIC AIMS

Aim 1: To stimulate gonadotropin secretion using exogenous kisspeptin.

Hypothesis: The inhibitory effect of hyperprolactinemia on GnRH secretion is mediated through kisspeptin. Therefore, kisspeptin administration to hyperprolactinemic women intolerant to conventional therapies will result in an increase in GnRH-induced gonadotropin release.

Aim 2: To stimulate folliculogenesis using exogenous kisspeptin.

Hypothesis: The suppression of folliculogenesis that occurs in hyperprolactinemia can be overcome by kisspeptin administration. Therefore, kisspeptin administration to hyperprolactinemic women intolerant to conventional therapies will result in mature follicle development.

SUBJECT SELECTION

This study will consist of two cohorts, one for each specific aim.

Inclusion/Exclusion Criteria

Inclusion:

- Female, Ages 18-45,
- Confirmed diagnosis by elevated levels of prolactin measured via blood test
- Physical Examination:
 - normal blood pressure, (systolic BP < 140 mm Hg, diastolic < 90 mm Hg).
- Laboratory Studies:
 - white blood cell, platelet counts, and TSH between 90% of the lower limit and 110% of the upper limit of the reference range,
 - hemoglobin no less than 0.5 gm/dL below the lower limit of the reference range for normal women,
 - BUN, creatinine, AST, ALT not elevated,
 - negative serum hCG pregnancy test at the time of screening (additional urine pregnancy test will be conducted prior to drug administration).
- Willing to complete a dopamine agonist washout period 6 ± 2 weeks prior to each of the frequent blood sampling visits (Cohort 1) or 6 ± 2 weeks prior to completing relevant screening labs until the end of the study (Cohort 2). The washout period will last at least 4 weeks.
- Not using oral contraceptives or willing to complete an oral contraceptive washout period 8 weeks prior to each of the frequent blood sampling visits (Cohort 1) or 8 weeks prior to completing relevant screening labs until the end of the study (Cohort 2).

Exclusion:

- Patients with a macroprolactinoma confirmed on MRI Imaging
- Current or recent use of a medication that, in the opinion of a study investigator, can modulate the reproductive axis

- History of a medication reaction requiring emergency medical care
- A medical condition that, in the opinion of a study investigator, would likely interfere with participation in/completion of the protocol
- Excessive alcohol consumption (>10 drinks/week) and/or use of illicit drugs
- Pregnant or trying to become pregnant
- Patients with a history of bilateral oophorectomy (ovaries were removed)
- Breast feeding

STUDY PROCEDURES

General Outline of Protocol

The goal of these studies is to assess the role of kisspeptin in GnRH and gonadotropin secretion as well as folliculogenesis in patients with hyperprolactinemia. GnRH cannot be measured in the peripheral circulation, and so LH will be measured as a surrogate marker of GnRH secretion. LH is secreted by the pituitary in direct response to GnRH, and there is a well-established one-to-one concordance between GnRH and LH pulses. ^{1,2}

Medication Washout

Cohort 2 subjects on dopamine agonists will be asked to complete a washout period 6±2 weeks prior to completing relevant screening labs and lasting until the end of the study. Cohort 2 subjects on oral contraceptive pills will be asked to undergo a washout period of 8 weeks prior to completing relevant screening labs and lasting until the end of the study. Subjects will be asked to discuss the washout with their prescribing physician prior to beginning washout. Any subjects who experience intolerable side effects as a result of medication washout will end participation in the study and be instructed to follow recommendations by their prescribing physician regarding resuming any medications.

Screening Visit

The screening visit will include a complete history and physical examination and blood tests (listed below). The total volume of blood drawn during screening will not exceed 18mL.

Screening laboratory tests

- Progesterone, Estradiol, Prolactin
- White blood cell count, platelet count, TSH, hemoglobin, BUN, creatinine, AST, ALT
- Serum hCG pregnancy test

Additional blood draws may be scheduled to repeat the progesterone and estradiol tests from the screening visit. This is to determine the phase of the menstrual cycle prior to subject's study visits. The volume of blood drawn is approximately 5 mL. The total volume of blood drawn will not exceed PHRC guidelines.

The screening history may be obtained by phone. Documentation of a physical examination performed by a non-study physician within the previous 12 months may be used in lieu of an in-person physical examination; in this case, a physical examination will also be performed by a study physician at Visit 1. To obtain physical examination results performed off-site, subjects will be given an MGH "authorization for disclosure of medical information from another facility" form. If a physical examination is performed solely for the purposes of this study, study funds will pay for the cost of the physical examination. Remote screening laboratory studies will be performed at MGH on a blood sample shipped by the subject or at a local laboratory site (e.g. LabCorp,

Quest, etc.); study funds will pay for all phlebotomy and shipping costs. Laboratory studies already performed within the previous 6 months will be in lieu of repeating screening studies unless abnormal.

Cohort 1 Protocol: Gonadotropin secretion (N=10)

Subjects will complete four outpatient visits. Procedures for each visit are described below:

Screening Visit: Described above

If eligibility criteria are all met, a member of the study team will call the subject and schedule them for two visits at the Clinical Research Center.

As mentioned above, we will ask subjects being treated with dopamine agonists to complete a washout period prior to the frequent blood sampling visit(s). The washout period will last at least 4 weeks.

Visit 1

- Admission to the Clinical Research Center (CRC)
- q10 minute blood sampling (3 mL q 10 min) x 12 hours without intervention to assess endogenous LH pulsatility. All samples will be assayed for LH. Progesterone (P4) will be measured on the first sample. FSH, prolactin, and estradiol (E2) will be assayed from pools of the frequent sampling studies.^{3,4}

Visit 2 (within 22 days of Visit 1)

- Admission to the Clinical Research Center (CRC)
- q10 minute sampling (3 mL q 10 min) x 12 hours
- Administration of 10 boluses of kisspeptin 0.313 µg/kg IV every hour beginning at hour 1 of the study. All samples will be assayed for LH. Progesterone (P4) will be measured on the first sample. FSH, prolactin, and estradiol (E2) will be assayed from pools of the frequent sampling studies.^{3,4}
- Administration of one bolus of GnRH 0.075 ug/kg IV at hour 11 of the study.

Visit 3: Final follow-up study visit

This visit will occur within a month after subjects have completed their Visit 2. The total blood drawn during this visit is 13mL. If any test result is abnormal, the subject will be followed until screening tests (CBC, BUN, creatinine, liver function studies) return to the ranges specified in eligibility criteria. If hemoglobin <10 g/dL then subjects will be provided with a one month supply of iron pills.

Cohort 2 Protocol: Folliculogenesis (N=5)

Subjects will complete 9 outpatient visits. Procedures for each visit are described below:

Screening Visit: Described above

If eligibility criteria are all met, a member of the study team will contact the subject to schedule Visit 1.

Visit 1: Day 1 of kisspeptin administration

- Participants will undergo a pelvic ultrasound to assess presence or absence of follicular growth. It is at investigator discretion to halt participation of any subject with evidence of follicular growth from the Visit 1 ultrasound.

- Participants will come to the Reproductive Endocrine Unit, or the CRC, where a study physician will initiate the administration of kisspeptin.
 - Option 1: Kisspeptin 0.313 – 13.19 µg/kg SC q60 – q240 minutes will be administered subcutaneously.
 - Option 2: Kisspeptin 0.313 µg/kg IV q 90 minutes will be administered using a closed IV system.
- Up to 10 blood samples will be drawn during the visit. One or more 3mL samples will be collected just before the initial kisspeptin is delivered and additional 3mL samples will be collected after the bolus is delivered, over the course of the next 80 minutes (maximum total blood collection volume of 30mL) to define the LH response to the kisspeptin. All blood samples will be assayed for LH. P4 will be measured on the first sample, and prolactin will be measured on both the first and final samples. Pooled samples will be used for measurements of FSH and E2. Time of day of sample collection will be recorded.
- Vital signs will be collected at least once during the visit.

Visits 2-7: Daily blood sampling (days 2-7 of kisspeptin administration)

- The GnRH-induced gonadotropin responses to a single bolus of kisspeptin (administered via pump(s)) will be monitored with up to 10 blood samples: One or more 3mL samples will be collected just before a kisspeptin bolus is delivered and additional 3mL samples will be collected after the bolus is delivered, over the course of the next 80 minutes, to define the LH response to the kisspeptin bolus. Maximum blood volume collected each day is 30mL . Sample collection will begin at the same time of the day ± 3 hours from the time collection began at Visit 1.
- All blood samples will be assayed for LH. P4 will be measured on the first sample, and prolactin will be measured on the first and final samples. Pooled samples will be used for measurements of FSH and E2. Time of day of sample collection will be recorded.
- Pelvic ultrasounds will be performed at Visit 3 or Visit 4 to monitor follicular growth. This ultrasound is intended to ensure that the rate of follicular growth and number of follicles do not indicate hyperstimulation, which is considered extremely unlikely to occur, based on prior data of kisspeptin administration in this dose range.
- Vital signs will be collected at least once during each daily visit.

Visit 8: Final Visit (day 8 of kisspeptin administration)

- At least 30 minutes after kisspeptin administration ends, participants will undergo final hormonal measurements: LH, FSH, E2, P4, prolactin; and safety laboratory studies: AST, ALT, BUN, Cr, hemoglobin, white blood cell, platelet counts, and TSH. The total blood drawn during this visit will not exceed 20mL.
 - The study team will contact participants if any safety value is outside the desired range (as stated in eligibility criteria) and arrange appropriate follow-up as needed. If hemoglobin <10 g/dL then subjects will be provided with a one-month supply of iron pills.
- Pelvic ultrasound will be performed to assess follicular growth.

Blood Draws:

Cohort 1: The total volume of blood drawn during screening will not exceed 18ml. The progesterone and estradiol tests drawn at screening may be repeated; approximately 5mL will be drawn. The study subjects will undergo two 12 hour sampling studies on two separate days, approximately 220mL will be drawn for each study. The total volume of blood drawn for final

follow-up is approximately 13mL. The total volume of blood drawn over the course of the protocol is within PHRC guidelines and will not exceed 550 mL.

Cohort 2:

The total volume of blood drawn during screening is 13-18mL. Subjects will then undergo daily monitoring blood draws over 7 days. Total volume of blood drawn during Visits 1-7 will not exceed 30mL each day. The total volume of blood drawn during Visit 8 will not exceed 20mL. The total volume of blood drawn over the course of the protocol is within the PHRC guidelines and will not exceed 550 mL.

If a study subject wants to participate in both Cohort 1 & Cohort 2, there will be a minimum of 8 weeks between study participation in Cohort 1 and participation in Cohort 2, to conform with PHRC guidelines.

Justification of doses:

Kisspeptin IV: The dose of kisspeptin 112-121 0.313 µg/kg (0.24 nmol/kg) IV x1 is the same dose used in the PI's studies in healthy men and women and is the dose predominantly used in the PI's studies of men with IHH. This dose was chosen based on the first reported use of kisspeptin in humans, which showed that doses smaller than this dose (using a molar equivalent) elicited a smaller response (rise in LH), whereas larger doses did not elicit a larger response.⁵ In other words, a dose of 0.24 nmol/kg was the smallest dose to elicit a maximal response. A more recent report of dose-response studies with kisspeptin made similar findings.⁶ The LH amplitudes of kisspeptin-induced-GnRH- induced LH pulses are comparable to the LH amplitudes observed endogenously during the follicular and luteal phases of the female menstrual cycle have LH amplitudes comparable to (follicular phase: kisspeptin induced LH amp 1.1 ± 1.0 vs. endogenous LH amp 1.2 ± 0.5 mIU/mL; mid-luteal phase: kisspeptin induced LH amp 4.0 ± 2.8 vs. endogenous LH amp 3.0 ± 1.5 mIU/mL)⁷ Moreover, in men, the range of LH amplitudes observed for kisspeptin-induced-GnRH-induced pulses overlaps the range of amplitudes that occurs endogenously (1.6 –10.9 and 0.5–7.8 mIU/ml, respectively).⁸ Thus, kisspeptin 0.24 nmol/kg (0.31 µg/kg) is a physiologic dose in healthy adults.

Kisspeptin SC: The dose range of kisspeptin 112-121 is 0.313 µg/kg (0.24 nmol/kg) – 13.19 µg/kg (10.1 nmol/kg). A range of doses is provided to account for a differential response of SC administration as compared to IV administration, as confirmed by the PI's other work.

GnRH: Long experience with GnRH has shown that a physiologic dose of GnRH is 25-75 ng/kg.⁹ To ensure that a response to GnRH is seen, the dose of GnRH 75 ng/kg IV x1 is used in these protocols. The dose used to achieve pituitary priming is GnRH 25 ng/kg SC q2h x6d, which has been shown to successfully achieve priming.¹⁰

Data suggests there is no interaction between kisspeptin administration and changes in prolactin levels in humans. Data recently published in Clinical Endocrinology show that prolactin levels are not significantly changed immediately following kisspeptin-54 injections (6.4 nmol/kg) in healthy women.¹¹ Our group has observed similar short term results after administration of single boluses of kisspeptin-10 (0.313 µg/kg; 0.24 nmol/kg) in healthy men and men with IHH. Long-term follow up data collected by our group in healthy men, cycling women, and postmenopausal women, as well as men and women with IHH, also show that prolactin levels do not significantly change after administration of boluses or infusions of kisspeptin-10.

Cohort 1 CRC Visits

Females will undergo a pregnancy test at screening and again at admission prior to receiving kisspeptin. Subjects will receive isovolumetric replacement with saline during blood sampling. Kisspeptin will be administered by a CRC RN. Vital signs (HR, BP, RR, and T) will be measured every 1-4 hours throughout the frequent sampling portions of the protocol and every 10 minutes for up to 30 minutes after kisspeptin administration.

Termination criteria will include: 1) blood pressure > 180 mmHg systolic or > 105 mmHg diastolic at any point during the protocol; 2) development or suspicion of an allergic or serious adverse reaction; 3) positive pregnancy test; 4) temperature $\geq 101.5^{\circ}\text{F}$ at any point in the study. Any subject who develops high blood pressure or an allergic reaction will receive follow-up inpatient medical care until the issue is resolved, with subsequent outpatient and/or phone follow-up as needed. The CRC is fully equipped to handle medical emergencies, with trained staff, a bag-valve mask in the room, a crash cart on the floor, and rapid access to a physician code team.

Cohort 2 daily blood sampling visits

Females will undergo a pregnancy test at screening and again prior to receiving kisspeptin. Kisspeptin will be administered via a pump(s). Vital signs (HR, BP, RR, and T) will be measured at least once during each daily blood sampling visit.

Termination criteria will include: 1) blood pressure > 180 mmHg systolic or > 105 mmHg diastolic at any point during the protocol; 2) development or suspicion of an allergic or serious adverse reaction; 3) positive pregnancy test; 4) temperature $\geq 101.5^{\circ}\text{F}$ at any point in the study. Any subject who develops high blood pressure or an allergic reaction will receive follow-up inpatient medical care until the issue is resolved, with subsequent outpatient and/or phone follow-up as needed.

BIOSTATISTICAL ANALYSIS

Assays

Given the long-term ongoing nature of this study, the assay methodologies employed to characterize the biochemical profile (both reproductive and metabolic) will be based on standard accepted methods as established by the Reproductive Endocrine Reference Laboratory. As such these methods may include immunoassays, measurement using standard laboratory platforms, radioimmunoassays, and mass spectroscopy. We anticipate that these methods will continue to evolve as the diagnostics field changes.

Cohort 1 (Specific Aim 1)

Population Size

Each patient will serve as her own control. The primary outcome will be the number of LH pulses on the first biochemical assessment (no kisspeptin) compared to the second assessment (+kisspeptin). Many studies in the literature have reported a decreased LH pulse frequency in hyperprolactinemia with one study (using q 10 minute sampling) documenting approximately 2.25 pulses / 12 h in hyperprolactinemic individuals.¹² During the second admission, by administering 10 boluses of kisspeptin, 10 LH pulses should be observed. For the purposes of these calculations however, 8 pulses will be conservatively estimated because some of those pulses will coincide with/conceal endogenous pulses. For a difference of 8 and an SD of 6.8, 10 subjects will need to be studied before and after kisspeptin to achieve 90% power at alpha = 0.05.

Data Analysis and Interpretation

LH pulses will be identified using a modified version of the Santen and Bardin method of pulse detection which has been validated *in vivo*.^{3,4} The primary outcome will be change in the frequency of LH pulses in response to kisspeptin administration. The hypothesis will be accepted if the change in LH frequency on kisspeptin is higher during intermittent kisspeptin administration (second assessment) than in the absence of kisspeptin administration. Mean LH level and LH pulse amplitude will also be calculated and used in secondary analyses.

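### Cohort 1 can rely on a hemoglobin up to 6 months old, with no count scheduled before about 440 mL is drawn at two visits; one count near Visit 1 is a cheap safety improvement

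*Combined protocol and SAP*

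**What the plan says.** All places are in the combined protocol and SAP.

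- **Inclusion criteria, Laboratory Studies:** the floor is "hemoglobin no less than 0.5 gm/dL below the lower limit of the reference range for normal women". It carries no date condition and applies to both cohorts.
- **Screening Visit:** hemoglobin is on the list of screening tests. Recent results may replace repeat testing: "Laboratory studies already performed within the previous 6 months will be in lieu of repeating screening studies unless abnormal". Hemoglobin is not exempted. The only repeat draw foreseen before the study visits is optional and hormonal: "Additional blood draws may be scheduled to repeat the progesterone and estradiol tests from the screening visit". When an outside physical examination is accepted, "in this case, a physical examination will also be performed by a study physician at Visit 1".
- **Cohort 1 Protocol:** "If eligibility criteria are all met, a member of the study team will call the subject and schedule them for two visits". No longest interval to Visit 1 is given. For dopamine agonists, "The washout period will last at least 4 weeks"; the inclusion criteria give 6 ± 2 weeks, and 8 weeks for oral contraceptives, both counted back from the sampling visits. Visits 1 and 2 list LH, progesterone, FSH, prolactin and estradiol, but no blood count. Visit 2 falls within 22 days of Visit 1, with no minimum gap.
- **Cohort 1 CRC Visits:** the pregnancy test is repeated at admission, saline replaces the volume drawn, and vital signs are monitored. The termination criteria do not mention hemoglobin.
- **Visit 3 and Blood Draws:** a count is checked within a month after Visit 2, with iron supplied below 10 g/dL. Each sampling study takes about 220 mL, and the protocol total is capped at 550 mL.

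**The concern.** The exception for abnormal results can only refer to the old result, because under the reuse rule no new one exists. A woman can therefore satisfy the hemoglobin criterion on paper, no longer satisfy it at Visit 1, and complete both sampling studies before anyone measures it. The protocol already refreshes other entry checks close to the procedures: pregnancy status for everyone, and the physical examination when an outside one was used. Hemoglobin, the entry laboratory value most directly affected by repeated sampling, is not refreshed.

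What is at stake is participant safety in a small cohort that the protocol says will not benefit directly. The primary outcome, the paired comparison and the sample size are not affected.

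**Working it through.** **1. Volume (reproduces the protocol's figure).** Sampling every 10 minutes for 12 hours gives 72 samples, or 73 with time zero. At 3 mL each this is 216 to 219 mL per study, against the stated 220 mL or so. Two studies take 2 × 219 = 438 mL (about 440 mL). The planned Cohort 1 maximum is 18 (screening) + 5 (optional hormone repeat) + 440 + 13 (Visit 3) = 476 mL, under the 550 mL cap.

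**2. Age of a reused value.** Counting the 6 months back from screening, the value is up to 26 weeks old at screening. If a full 8-week washout then follows, it is 26 + 8 = 34 weeks old at Visit 1 and 34 + 22/7 ≈ 37 weeks at the latest Visit 2. Since no maximum interval is stated, 34 weeks is an example and not a ceiling. If the 6 months is counted to Visit 1 instead, the figure there is 26 weeks.

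**3. Size of the effect: illustration only.** The documents give no reference limit, rate of hemoglobin change, body weight, blood volume or red-cell recovery. Assume:
- a lower reference limit of 12.0 g/dL, so a floor of 11.5;
- an unseen fall to 11.0;
- blood volume of 60–70 mL/kg and weight of 45–80 kg;
- saline replacement throughout and no red-cell recovery between visits.

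Then final Hb = starting Hb × exp(−438 / (mL/kg × kg)). From 11.0 g/dL:

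| Weight | 60 mL/kg | 65 mL/kg | 70 mL/kg |
|---|---|---|---|
| 45 kg | 9.35 | 9.47 | 9.57 |
| 50 kg | 9.51 | 9.61 | 9.71 |
| 60 kg | 9.74 | 9.83 | 9.91 |
| 70 kg | 9.91 | 9.99 | 10.06 |
| 80 kg | 10.04 | 10.11 | 10.17 |

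The weight at which 11.0 ends at exactly 10.0, the protocol's iron trigger, is 438 / (mL/kg × ln 1.1) = 76.6, 70.7 and 65.7 kg at 60, 65 and 70 mL/kg. If half of the Visit 1 loss is recovered before Visit 2, it falls to 57.1, 52.7 and 49.0 kg. With full recovery, the final value is 10.14 to 10.58 over the whole range, so nobody starting at 11.0 ends below 10.

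**4. Comparison with women who do meet the floor.** With no recovery, a reused 12.0 that is still true ends at 10.20 to 11.10. At 60 kg and 65 mL/kg, a fresh 11.5 ends at 10.28, against 9.83 from 11.0, a difference of 0.45 g/dL. A light woman with a fresh 11.5 can still end below 10: 9.78 (45 kg) and 9.94 (50 kg) at 60 mL/kg, and 9.90 (45 kg) at 65 mL/kg.

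**5. What a Visit 1 check leaves open.** A count taken 30 days before Visit 1 is up to 30 + 22 = 52 days old at Visit 2, with one study of 219 mL in between. With no recovery at 65 mL/kg, a woman at 11.5 at Visit 1 enters Visit 2 at 11.5 × exp(−219 / (65 × kg)) = 10.67 (45 kg) to 11.03 (80 kg).

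**The case against.** The strongest reply is that nothing here is inconsistent. Reuse is permitted rather than required, it applies only to results that were normal, and women without recent results get fresh ones. The total volume is stated to lie within the institution's guidelines. Saline, vital signs, emergency cover, a Visit 1 examination when an outside one was used, the investigator's discretion to exclude on medical grounds, and follow-up with iron all reduce the consequences. How recent a laboratory value must be is a design preference. All of this stands, and it is why the point is modest. It does not remove the gap, because none of these measures hemoglobin before the draws.

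A second reply is that the harm depends on stacked assumptions: a fall, low weight and incomplete recovery. That also stands. The illustration shows only what could happen under those assumptions. The 10 g/dL benchmark is the protocol's trigger for iron, not a stated threshold of harm, and ending below it is not peculiar to old laboratory values.

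A third is that a check before Visit 1 leaves Visit 2 unconfirmed. That is correct and should be said openly. Applying the entry floor again at Visit 2 could, on the same model, exclude women who were eligible at Visit 1 and lose completed Visit 1 data from a paired analysis of 10. The floor is written as an entry criterion, and the proposal keeps it as one.

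A reader might infer that the floor was set to guard against this blood loss. The documents do not say so: it sits among general laboratory criteria for both cohorts, including Cohort 2, which draws at most 30 mL a day.

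**Conclusion.** The point holds as a low-cost safety improvement of modest severity, not as an error in the plan. What rests on the text alone is this: a normal hemoglobin up to 6 months old can satisfy eligibility, no limit is set on the time from screening to Visit 1, and no further Cohort 1 count is scheduled until about 440 mL has been drawn. A woman who has since dropped below the floor would go undetected until then.

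The size in g/dL rests on the assumed reference limit, fall, weight, blood volume and recovery. Within those ranges, a true 11.0 ends between 9.35 (45 kg, 60 mL/kg, no recovery) and 10.58 (80 kg, 70 mL/kg, full recovery).

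Two further inferences should be resisted. One is that such a fall is likely: the documents give no rate of change, so no probability can be attached. The other is that a fresh check would catch most women who would end below 10 g/dL: that needs a joint distribution of weight and hemoglobin, which the documents do not supply.

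**What to change.** Add to the Screening Visit section:

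> For Cohort 1, hemoglobin is exempt from the 6-month rule. A hemoglobin drawn within 30 days before Visit 1 (for example with the optional progesterone/estradiol draw), or at Visit 1 admission if none is available, must meet the hemoglobin inclusion criterion before frequent sampling starts.

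The threshold is the existing one. The 30-day window is a proposal with no source in the documents; the sponsor may prefer another short interval. A fresh screening value inside the window already satisfies it. No Visit 2 check is proposed.

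**Cost.** Two sentences and at most one added count per woman, 10 in all. Assuming a 3 mL tube, the planned maximum rises from 476 to about 479 mL, under the 550 mL cap. A woman not having the optional hormone draw needs one extra draw or the admission check. Endpoint, power and the 22-day window are unchanged, and no completed Visit 1 is lost.

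The main downside is an occasional woman found ineligible during or after washout. With a draw 30 days before Visit 1, a 4-week (28-day) washout has not started, a 6-week one is 42 − 30 = 12 days in, and an 8-week one is 56 − 30 = 26 days in. With the admission check, the full 28, 42 or 56 days have been spent and sampling waits for the result, so the earlier draw is preferable.

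### Does the 80-minute LH sampling window in Cohort 2 need a written rule for SC dosing intervals shorter than 80 minutes?

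*Combined protocol and SAP*

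**What the plan says.** The relevant text is in the Cohort 2 Protocol.

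- **Dosing (Visit 1).** Under Option 1, kisspeptin "SC q60 – q240 minutes will be administered subcutaneously". Option 2 is IV every 90 minutes.
- **Sampling at Visit 1.** "Up to 10 blood samples will be drawn during the visit", with the post-dose samples spread "over the course of the next 80 minutes (maximum total blood collection volume of 30mL) to define the LH response to the kisspeptin".
- **Sampling at Visits 2-7.** "The GnRH-induced gonadotropin responses to a single bolus of kisspeptin (administered via pump(s)) will be monitored with up to 10 blood samples". One or more samples come just before a bolus, and the others follow "over the course of the next 80 minutes, to define the LH response to the kisspeptin bolus".
- **Assays at Visits 2-7.** LH is measured in every sample. In addition, "prolactin will be measured on the first and final samples" and "Pooled samples will be used for measurements of FSH and E2". On timing, "Time of day of sample collection will be recorded".
- **Analysis.** Under Biostatistical Analysis, the Cohort 2 text gives follicular growth between Visits 1 and 8 as the primary endpoint and a sample-size statement for maximum follicle size. It names no LH measure. Mean LH and pulse amplitude appear as secondary measures only in the Cohort 1 text.

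**The concern.** The stated purpose at Visits 2-7 is to describe the response to one bolus, yet the window is longer than the shortest permitted interval. The 60-minute interval is the written lower limit of the range, so this is not a contrived case. No sentence ends sampling at the next bolus, holds that bolus, or excludes later samples from the summary.

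If such an interval is used and all samples are kept, a mean or area over 80 minutes would mix the tail of one response with the start of the next. A peak reached before the next bolus would not change. Women dosed at different intervals would have summaries that do not mean quite the same thing, and with five women there is little room to absorb that. The same draws feed the pooled FSH and E2 and the last prolactin value, so those might also include material from after a second bolus.

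**Working it through.** The plan gives no figure of its own on this point, so the check is interval arithmetic followed by a look at what depends on the result.

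**Inputs.** Window W = 80 minutes (Visit 1 and Visits 2-7 text). SC interval q = 60 to 240 minutes and IV interval 90 minutes (Visit 1, Options 1 and 2). Five women (Cohort 2 heading).

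**Step 1: overlap.** Minutes of the window after the next bolus = max(0, 80 − q), and share = that / 80.

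| Interval q (min) | Minutes after next bolus | Share of window |
|---|---|---|
| 60 | 20 | 25% |
| 65 | 15 | 18.75% |
| 70 | 10 | 12.5% |
| 75 | 5 | 6.25% |
| 80 or longer, including IV 90 | 0 | 0% |

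Only one further bolus can fall inside the window, because a second could come no sooner than 2 × 60 = 120 minutes. These are shares of time. They are not shares of the LH response, because no response latency is given.

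**Step 2: how many windows.** The single-bolus wording covers 5 women × 6 visits = 30 windows. That is a ceiling. How many would use an interval under 80 minutes is not stated, and it may be none. Visit 1 is worded as the response to the kisspeptin, without the single-bolus qualifier.

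**Step 3: how many samples.** Neither the number nor the spacing is fixed. At most 9 samples can follow the bolus, since up to 10 include at least one before it. Assume n evenly spaced post-bolus samples ending at 80 minutes, with a sample due exactly at the next bolus counted as before it. At q = 60 the late samples are then:

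- n = 2 (40, 80 min): 1/2
- n = 4 (20, 40, 60, 80 min): 1/4
- n = 5 (16, 32, 48, 64, 80 min): 2/5
- n = 8 (every 10 min): 2/8
- n = 9 (every 8.9 min): 3/9

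The share runs from 25% to 50% across these choices alone, and it is 0 if the site stops before the next bolus. No single figure for affected samples can be defended.

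**Step 4: what depends on it.**

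- *Primary endpoint and sample size.* These rest on a follicle-size difference of 7.8 mm, an SD of 4.4 and N = 5. No LH value enters.
- *LH.* Each sample has its own LH value and a recorded collection time. Boluses at Visits 2-7 are delivered by pump, so next bolus time = index bolus time + q. Samples later than that can be identified and left out of a single-bolus summary without losing data.
- *Pooled FSH and E2.* A physical pool cannot be separated afterwards. At Visits 2-7, however, it is drawn after one to six days of repeated boluses, so it could not isolate one bolus at any permitted interval, including 240 minutes.
- *Prolactin.* The Justification of doses section reports data showing no significant change in prolactin after kisspeptin. Whether the last sample follows one bolus or two is then a matter of labelling.

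**The case for a change.** The strongest case for acting is that intent is not a rule. The text requires sample times but does not expressly require bolus times, and without both, late samples cannot be reliably separated. The plan's own reasoning for Cohort 1 expects ten hourly boluses to give ten LH pulses, so a bolus at 60 minutes should be expected to produce its own rise. A few sentences would settle the matter, with no added visits or blood.

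Part of this stands. The overlap exists, no handling is written down, and recovery of bolus times from the pump schedule is an inference. A sentence on it would do no harm.

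The rest does not carry the point to a change. The Cohort 1 expectation also treats hourly responses as separable, so a second bolus inside a window does not make the earlier samples uninterpretable. It concerns IV dosing too, and the Justification of doses section itself allows that SC responses differ. The two texts can both be met as written: the number of samples is a maximum and no sample times are fixed, so a site may finish before the next bolus. Imposing one common shortened window would cost up to 20 minutes of response in women whose own window holds no second bolus. Cutting at the next bolus would still leave the influence of earlier boluses at Visits 2-7, which only the pre-bolus samples address.

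**Conclusion.** No change to the plan is called for. At SC intervals under 80 minutes the window can run past the next bolus by up to 20 minutes (25% at the 60-minute limit). This affects a descriptive LH measure that no Cohort 2 analysis uses. Follicular growth, N = 5, the IV option and SC intervals of 80 minutes or longer are unaffected. Whether any reported value would move is unknown, because the intervals used, the sample times and the LH summary are all unstated.

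The gap is one that analysts fill sensibly: told to describe the response to one bolus, they use LH values drawn before the next one. This rests on two assumptions: the pump schedule is available, so that bolus times can be placed against sample times, and Cohort 2 LH stays descriptive. If an LH summary were made a tested endpoint, or compared between women dosed at different intervals, the handling of late samples would need to be written down. Nothing here favours one permitted interval over another.
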